14.2.4 Recording and Reporting of Adverse Events

The site investigator is responsible for monitoring the safety of participants enrolled into the study at the study sites. The investigator will probe, via discussion with the participant, for the occurrence of AEs during each study visit and record the information in the site's source documents. Participants will be instructed to report the occurrence of potential AEs between visits (on a weekly basis) using the Electronic Data Capture (EDC) system. The investigator will receive an email notification and will call the participant to gather further information about the AE(s).

The investigator will record selected AEs on the eCRF. Adverse events will be described by duration (start and stop dates), severity, outcome, and relationship to study drug. Adverse events will be reported to the Data Safety Monitoring Board (DSMB), Duke IRB and/or other agencies according to guidelines established by those entities/agencies. All AEs that are identified, whether or not listed in Section 14.2.1, will be followed by the site until resolution or stabilization. Adverse Events will be captured from the time of consent through the Month 6 visit.

14.3 Data Safety Monitoring Board

The DSMB will be composed of 4 members: a physician, a statistician, a patient representative, and a bioethicist. All DSMB operations will be managed by the DCRI.

The goal of the DSMB will be to monitor patient safety and to review the performance of the study. The DSMB will be responsible for providing recommendations regarding trial's conduct and guidance to ensure the safety and well-being of patients treated by study physicians. A separate DSMB charter will outline the operating guidelines for the committee, the protocol for evaluation of data, and data tables to be provided. The charter will be created prior to study enrollment and agreed upon during the initial meeting of the DSMB. It is anticipated that the DSMB will meet at 6-month intervals to review the accumulating data for safety.

DSMB Analyses: A DCRI Statistical Analyst and Programmer will generate the analyses required by the DSMB charter and provide these in advance of each DSMB meeting. This individual will ensure high quality and timely reports are submitted. Confidential Interim Data Reports will be prepared regularly by the DSMB statistician as specified in the Charter. The report will include recruitment and retention rates, SAEs, and other information as requested by the DSMB Chair.

15 STATISTICAL CONSIDERATIONS

15.1 VBD Subtype Designation

Women with VBD-c will be distinguished from those with VBD-p based on the presence of a COPC. The Institute of Medicine's 2011 report, *Relieving Pain in America*, identified 9 COPCs that predominantly affect women and frequently co-occur with VBD.⁹³ The presence of a COPC will be determined using the COPC survey. This is an easy-to-complete form including modules with check-box questions and a body mannequin to determine the presence of 9 COPCs: 1) FMS, 2) TMD, 3) back pain, 4) IBS, 5) chronic tension-type headache, 6) chronic migraine, and 7) chronic fatigue syndrome, 8) endometriosis, and 9) interstitial cystitis. Women with VBD and no COPCs will be designated as VBD-p, while women with VBD and ≥ 1 COPC will be designated as VBD-c. These criteria will be used as a primary method to distinguish between VBD-p and VBD-c in this study.

We, however, acknowledge that the criteria to distinguish VBD subtypes needs further exploration. In particular, it is possible that the optimal cutoff for VBD-c requires more than one COPC to be present. Therefore, as a secondary method to characterize VBD subtypes, we will calculate a continuous COPC 'centralness' score defined as the number of COPCs present ranging from 0 to 9. This continuous COPC score will be used to identify the optimal cutoff value between VBD-p and VBD-c in terms of treatment response.

To further characterize the two VBD subtypes, we will also measure generalized pain at 'neutral' non-pelvic sites using a quantitative sensory testing approach designed by [name] and colleagues.^{94, 95} The 3 neutral sites (deltoid muscle, shin, trapezius) are remote from the pelvic region and not used for diagnosing other pain conditions, but reflect an individual's overall

pressure pain sensitivity.⁹⁸⁻¹⁰⁰ An algometer will be applied to the 3 sites, with continuously ascending pressure at a rate of 1 kg/s to a maximum of 10 kg. Participants will indicate when the evoked sensation first becomes painful. A composite pressure pain threshold (PPT) score will be compared between VBD-c and VBD-p subgroups using ANCOVA. We would expect women with VBD-p to have higher PPT scores (less pain) and women with VBD-c to have lower scores (more pain) at these sites.

15.2 Analysis of the Aim 1 Endpoints

Primary endpoints will be the net change in vaginal vestibule pain following treatment measured using the Tampon Test and the Short-Form McGill Pain Questionnaire (SF-MPQ).

- The Tampon Test will provide a self-reported numeric rating scale of pain with self-tampon insertion, performed by the patient and reported to the research nurse. An Original Regular Tampax tampon will be inserted by the participant into her vagina and then she will be asked to verbally rate the pain on a scale of 0-10, with 0 meaning no pain and 10 meaning the worst possible pain. The Tampon Test has good reliability, construct validity, and responsiveness and is a recommended outcome measure for VBD clinical trials.⁹⁶
- The SF-MPQ measures perceived sensory qualities of pain using 11 descriptors and affective qualities related to pain using 5 descriptors. Responses on 4-point scales are summed to compute scores for each section.⁹⁷ SF-MPQ subscales have been successfully used to quantify treatment responses in trials for VBD and vulvodynia.⁹⁸⁻¹⁰⁰

Secondary endpoints include changes in pressure pain thresholds (PPTs) measured at the

- Vaginal Vestibule PPT will be determined using a digital vestibular algometer applied to 3 externally-accessed sites (2 and 10 o'clock on the upper vestibule and 6 o'clock on the lower vestibule) beginning at 1N and increasing until the participant's first sensation of pain or a maximum applied pressure of 10N.¹⁰²
- Levator Muscle Complex PPTs will be determined in a similar manner by applying the algometer internally to the right, midline, and left puborectalis levator muscles sites (5, 6, and 7 o'clock) just lateral to the perineum.
- Remote Bodily PPTs will be determined in a similar manner by applying the algometer to 3 'neutral' non-pelvic body sites (deltoid, shin, and trapezius), right and left, and calculating a composite score.

Data Analysis. The two primary statistical questions for Aim 1 are: 1a) Is peripheral treatment with lidocaine/estradiol compound cream, or central treatment with nortriptyline, or a combination of both treatments more effective for either VBD subtype than placebo? 1b) Is peripheral treatment more effective than central treatment in VBD-p, and is central treatment more effective than peripheral treatment in VBD-c?

To answer questions 1a and 1b, we will fit mixed model repeated measures (MMRM) models which account for missing data as an integral part of the analyses under the assumption of ignorable missing. To answer question 1a, the MMRM model includes longitudinal pain score (0-10 NRS on Tampon Test) as a continuous outcome variable; includes fixed effect terms for treatment (nortriptyline, lidocaine/estradiol, and their interaction), visit, treatment visit interaction, center, and fixed effect covariates vector including age, VBD subtype (binary variable where VBD-c is coded as 0 and VBD-p coded as 1), race (three levels "white", "black" and "other" race, coded into two binary dummy variables with European American serving as a reference level).

Overall treatment effect of nortriptyline, lidocaine/estradiol, and their interaction will be evaluated using an F-test. If significant ($p < 0.05$), treatment differences (each of 3 treatment groups minus placebo) in the Least-Squares means (LS means), their 2-sided 95% CIs, and associated p-

values will be estimated from the MMRM model. P-values will be compared with the significance threshold Bonferroni-corrected for 3 tests (i.e. alpha 0.0166).

To answer question 1b, we will fit a MMRM model analogous to 1a, with additional terms of VBD subtype visit interaction, treatment VBD subtype interaction, and treatment visit VBD subtype interaction. The significance of the additional interaction terms will be evaluated using a F-test comparing the full model in 1b and the reduced model in 1a. Significant ($p < 0.05$) F-test will suggest that the effect of either nortriptyline or lidocaine/estradiol cream, or both, differ by VBD subtype. In this case, we will compare the LS means of the treatment differences in each treatment-VBD-subtype subgroup, after appropriate Bonferroni correction.

If the results for question 1a or 1b are statistically significant, the following primary outcomes will be analyzed using the same modeling strategies (models in 1a and 1b above): % decrease in pain score (tampon test) from baseline to the 16-week time point and % decrease in perceived pain on the SF-MPQ from baseline to the 16-week time point. Secondary outcomes include change in mucosal, vulvovaginal muscle, and remote bodily PPTs from baseline to the 16-week time point. Secondary outcomes also include change in pain scores and PPTs from baseline to the 8-week time point and change in pain scores and PPTs from the 16-week to the 24-week time point.

If the result for question 1b is non-significant, we will use the continuous COPC score in model 1b instead of a dichotomous VBD classification to compare treatment success for VBD-p and VBD-c. In addition, we use a binary treatment outcome (achievement of 30% pain reduction) to identify the optimal cutoff of the continuous COPC score in each treatment group.

Secondary analyses of muscle pain based on PPTs will also determine: a) the proportion of women with VBD that have a pelvic muscle pain component; b) differences in the distribution of muscle pain in VBD-p and VBD-c groups; and c) presence of muscle pain to predict treatment outcome. The latter will be tested by including the muscle pain variable (continuous or dichotomous) as part of the fixed effect term in model 1a.

Expected Outcomes. **1)** For women with VBD-p, peripheral lidocaine/estradiol treatment will be more effective than placebo or nortriptyline in reducing numeric pain ratings on the tampon test, perceived pain on the SF-MPQ, and pelvic PPTs on the algometer test at week 8 and week 16. **2)** For women with VBD-c, centrally-targeted nortriptyline treatment will be more effective than placebo or lidocaine/estradiol in reducing numeric pain ratings on the tampon test, perceived pain on the SF-MPQ, and pelvic/remote bodily PPTs on the algometer test at week 16. **3)** For women with VBD-c, combined peripheral and centrally-targeted treatments will be most effective in reducing pain on primary and secondary outcome measures at week 16. **4)** The two VBD subtypes will exhibit differential responses to treatment withdrawal at week 16, such that at the week 24 visit women with VBD-c will exhibit increases in pain after treatment withdrawal compared to women with VBD-p.

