10.1 Baseline Evaluation

Baseline procedures and assessments (described in detail in **Section 15** below) will be performed in the following order:

- Participant consent
- Tampon test with 0-10 NRS
- Blood collection and processing
- Participant questionnaires:
 - Demographics
 - Social history
 - Gynecological history
 - VPAQ
 - PROMIS BPSFS-F
 - COPC inventory
 - SF12v2
 - SCL-27
 - PILL
 - PSS
 - Sleep scale
- Remote bodily PPTs (deltoid, shin, trapezius)
- Qualitative pelvic sensory testing
- Vaginal sample collection
- Local vestibular PPTs (5, 6, and 7 o'clock)

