11.2 Visit 3 (16-Week)

Upon arrival, participants will return any remaining study medication to the research team. Study medication will be discontinued.

The week 16 visit procedures and assessments will be performed in the following order:

- Tampon test with 0-10 NRS
- Blood collection and processing
- Participant questionnaires:
 - VPAQ
 - PROMIS BPSFS-F
 - COPC follow-up survey
 - SF12v2
 - SCL-27
 - PILL
 - PSS
 - Sleep scale
- Remote bodily PPTs (deltoid, shin, trapezius)
- Qualitative pelvic sensory testing
- Vaginal sample collection
- Local vestibular PPTs (5, 6, and 7 o'clock)

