12 OUTCOME DETERMINATIONS

Aim 1. Determine the efficacy of peripheral, central, and combined treatments in alleviating pain among women with VBD-p and VBD-c.

Primary Endpoints:

- Ia. pain score during tampon test at 16 weeks
- Ib. self-reported pain *via* SF-MPQ at 16 weeks

Secondary Endpoints:

- Ila. experimental pain *via* local and remote PPTs at 16 weeks
- Ilb. COPC pain levels *via* COPC follow-up survey at 16 weeks
- Ilc. Pain scores and PPTs at 8 weeks and 24 weeks

Aim 2. Determine the efficacy of peripheral, central, and combined treatments in improving patient reported outcomes among women with VBD-p and VBD-c.

Primary Endpoints:

- Ia. self-reported physical/mental health *via* SF12v2 at 16 weeks
- Ib. sexual health *via* PROMIS at 16 weeks

Secondary Endpoints:

- Ila. mood *via* SCL-27 at 16 weeks
- Ilb. somatic awareness *via* PILL at 16 weeks
- Ilc. perceived stress *via* PSS at 16 weeks
- Ild. sleep *via* sleep scale at 16 weeks
- Ile. Patient reported outcomes at 8 weeks and 24 weeks

Aim 3. Determine the efficacy of peripheral, central, and combined treatments in normalizing cytokine and microRNA expression profiles in vaginal and blood tissues collected from women with VBD-p and VBD-c.

Primary Endpoints:

- Ia. cytokine levels *via* mesoscale discovery assays at 16 weeks
- Ib. microRNA levels *via* sequencing read at 16 weeks

Secondary Endpoints:

- Ila. cytokine and microRNA levels at 8 weeks and 24 weeks
- Ilb. Aim 3 will also identify cytokine and microRNA biomarkers at baseline that predict treatment response at 8, 16, and 24 weeks

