15.3 Analysis of the Aim 2 Endpoints

Primary endpoints include the net change in perceived sexual health measured using the Patient-Reported Outcomes Measurement Information System (PROMIS) and perceived physical and mental health measured using the SF-12 Health Survey (SF-12).

- The PROMIS is a 96-item form developed by the NIH that measures 11 domains of biopsychosocial function and includes an assessment of sexual function measures (e.g., desire, frequency, fear, and pain) related to sexual intercourse.¹¹⁵
- The SF-12 assesses 6 domains: global health, physical functioning, physical roles, emotional functioning, emotional roles and pain interference using an algorithm¹¹⁸ based on answers to 12 physical and mental health-related questions.

Secondary endpoints include net changes in perceived mood and health using:

- Symptom Check List 27 (SCL-27), which measures a broad range of psychological symptoms (e.g., anxiety and depression) and has high reliability and strong correlations to pain.^{121,122}
- Pennebaker Index of Limbic Languidness (PILL), which is used to create a summary score of somatic symptoms (e.g., itchy eyes, dizziness). Symptom frequency is recorded on a five-point Likert scale ranging from “never” to “more than once a week”.¹⁰⁸
- Perceived stress scale (PSS), which is a 10-item scale that measures the impact of personal stress on thoughts and feelings.
- Sleep Scale, which is a 12-item scale that measures amount of sleep and ease/difficulty of initiating and maintaining sleep

Data Analysis. The two primary statistical questions for Aim 2 are: 2a) At baseline, do women with VBD-c exhibit worse perceived physical, mental, or sexual health than women with VBD-p? 2b) Considering physical, mental, or sexual health, is peripheral treatment with lidocaine/estradiol cream more effective than nortriptyline in VBD-p, and central treatment with nortriptyline more effective than lidocaine/estradiol cream in VBD-c?

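### The SF-MPQ is an Aim 1 primary endpoint that Section 4 says is measured at four visits, but every visit list and the schedule of assessments omit it

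*Combined protocol and SAP*

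**What the plan says.** Four parts of the protocol require the SF-MPQ.

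- Sections 2 and 12 list Aim 1 primary endpoint Ib as "self-reported pain *via* SF-MPQ at 16 weeks".
- Section 4 says the Aim 1 hypothesis will be tested with tampon-test pain and the McGill questionnaire at baseline and at 8, 16 and 24 weeks.
- Section 15.2 says the primary endpoints are "measured using the Tampon Test and the Short-Form McGill Pain Questionnaire (SF-MPQ". It describes 11 sensory and 5 affective descriptors, summed to one score per section.
- Section 15.2 later plans to analyse the percent "decrease in perceived pain on the SF-MPQ from baseline to the 16-week time point".

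The operational parts do not list it. Section 10.1 says the baseline procedures "will be performed in the following order", and Section 11.2 says "The week 16 visit procedures and assessments will be performed in the following order". Neither list names the SF-MPQ. Sections 11.1 and 11.3 and Appendix A do not name it either, although Sections 5.3 and 5.4 describe Appendix A as the complete schedule. All of them carry a VPAQ.

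Two further passages bear on the smaller points. Section 15.3 states that "The PROMIS is a 96-item form developed by the NIH that measures 11 domains of biopsychosocial function", and takes PROMIS trait scores as secondary outcomes, while the only PROMIS form scheduled is the BPSFS-F. Section 15.2 measures the vestibular pressure pain threshold (PPT) with "a digital vestibular algometer applied to 3 externally-accessed sites (2 and 10" o'clock, and 6 o'clock), whereas Section 11.2 lists "Local vestibular PPTs (5, 6, and 7" o'clock).

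**The concern.** Coordinators build their visit packets and eCRFs from the visit lists and the schedule, not from the aims or the analysis section. If those are followed, a named primary endpoint is never recorded. A missing baseline pain score cannot be repaired, because a pre-treatment rating cannot be obtained once treatment has begun. There is a second risk. If the gap were found only at analysis, the VPAQ would be the obvious substitute, and a primary score chosen from it after unblinding would be post hoc.

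**Working it through.** This is a question of what is collected, so there is no plan figure to reproduce. The check sets each endpoint instrument against each place where collection is specified.

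**Step 1. What the analysis needs.** Percent decrease = 100 × (S0 − S16) / S0, where S0 and S16 are a woman's SF-MPQ scores at baseline and week 16. Both are required.

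**Step 2. Where the SF-MPQ is collected.**

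| Place | Content | SF-MPQ listed? |
|---|---|---|
| Section 10.1, baseline | 11 questionnaire entries | No |
| Section 11.1, week 8 | 8 questionnaires | No |
| Section 11.2, week 16 | same 8 | No |
| Section 11.3, week 24 | same 8 | No |
| Appendix A | 24 rows | No |

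That is 0 of 4 visit lists and 0 of 24 rows. Neither S0 nor S16 has a collection point.

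**Step 3. Is this a general looseness in the lists?** No. Seven other questionnaires support endpoints: SF12v2, PROMIS (as the BPSFS-F), SCL-27, PILL, PSS, the sleep scale and the COPC follow-up survey. All seven are on the three follow-up lists and in Appendix A. All have a baseline form, the COPC inventory serving that purpose for the COPC survey. The SF-MPQ is the only questionnaire endpoint with no collection point, and it is a primary one.

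**Step 4. What the VPAQ is.** It is on all four lists and in Appendix A. It is absent from the abbreviation list in Section 1.1, is not described in Section 15, and is named in no endpoint or model.

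**Step 5. What does not depend on the SF-MPQ.** The model for questions 1a and 1b uses the 0–10 tampon-test rating as its outcome. The Aim 1 power statement in Section 15.6 rests on a 0–10 scale with SD 2.0. The tampon test is scheduled at screening (week 0) and at weeks 8, 16 and 24.

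**Step 6. PROMIS.** Section 1.1 expands BPSFS-F as a brief sexual function and satisfaction profile, and it is given at every visit, so the sexual-health primary endpoint of Aim 2 has data. No other PROMIS form is scheduled as a source for the trait scores in Section 15.3, and those scores are not among the Section 12 endpoints.

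**Step 7. PPT positions.** Section 15.2 puts the vestibule at 2, 10 and 6 o'clock and the levator at 5, 6 and 7. The visit lists put the vestibule at 5, 6 and 7. The two vestibular sets share only 6 o'clock, and the listed set is the one Section 15.2 gives to the levator. Appendix A has separate vestibule and levator rows, both marked at baseline and weeks 8, 16 and 24, but gives no positions.

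**The case against.** The strongest reply is that the protocol does provide for collection. Section 4 names the instrument and all four time points, Section 10.1 refers the reader to Section 15 for detail, and Section 15.2 describes the SF-MPQ. Sections 5.3 and 10 also call for questionnaires on perceived pain. This stands to the extent that the intention to collect is clear. A reader might infer from the visit lists that the SF-MPQ endpoint is lost and cannot be analysed. The documents do not support that, because they point both ways. But the general wording names no instrument, and Section 10.1 sends the reader to Section 15 for detail on procedures it has listed, which do not include this one.

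A second reply is that the VPAQ may contain the McGill items. It may, and equally it may replace or merely accompany them. A reader might infer that it is being collected in place of the SF-MPQ, but the documents neither say this nor plan any substitution.

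Third, the damage is bounded. The tampon-test model carries the main Aim 1 inference, and Section 15.2 runs the SF-MPQ analysis only if question 1a or 1b is significant. This is correct and limits the consequence, but the SF-MPQ is still designated primary.

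Fourth, the PROMIS and PPT mismatches might be read as the same fault. They are not: the sexual-health primary endpoint is collected, and vestibular and levator PPTs are both scheduled at every visit.

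**Conclusion.** The protocol contradicts itself on collection of an Aim 1 primary endpoint. Sections 2, 4, 12 and 15.2 require the SF-MPQ, while Sections 10.1 and 11.1 to 11.3 and Appendix A omit it at all four visits. The affected endpoint is one of the two Aim 1 primaries. The planned percent decrease could not be computed for any woman seen at a site that follows the lists and the schedule. How many of the planned 400 that would be depends on site practice, which the documents do not show.

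The conclusion assumes that the VPAQ does not already supply the SF-MPQ items; if it does, the fault is an undocumented source and scoring rule. The Section 6 flow diagram is not in the text checked here. If it lists the SF-MPQ, that would add to the contradiction and not resolve it.

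This must be fixed because the endpoint is primary and its baseline cannot be recovered later. The PROMIS trait scores and the PPT clock positions are minor points affecting secondary outcomes only.

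**What to change.** Choose one of two routes, while the trial is still blinded.

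1. Add the SF-MPQ to Sections 10.1 and 11.1 to 11.3 and to the baseline, week 8, week 16 and week 24 columns of Appendix A. State which score is primary (sensory, affective or total), since Section 15.2 defines section scores without choosing one. Define the VPAQ and say what it is for.
2. If the VPAQ supplies the SF-MPQ items, say so and give the scoring. If it replaces the SF-MPQ, amend Sections 2, 4, 12 and 15.2 to a named VPAQ score.

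If women have already been enrolled without the form, record how many lack a baseline SF-MPQ score.

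In the same amendment, make Section 15.3 agree with the BPSFS-F, either by scheduling a source for the PROMIS trait scores or by removing them. Also make the vestibular PPT positions the same in Section 15.2 and the visit lists.

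The cost is a protocol amendment plus, under route 1, a form of 11 + 5 = 16 descriptors at each of four visits (64 ratings per woman). Route 2 costs wording only.

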5.3 Baseline Evaluation Phase and Randomization

Immediately following screening, research participants will complete all baseline assessments, including 1) completion of validated questionnaires to measure perceived pain, health, mood, and sexual function 2) vulvar exam and quantitative sensory testing to measure pressure pain thresholds at local (vaginal) and remote body sites, and 3) collection of biologic samples to measure local (vaginal) and systemic (blood) cytokines and miRNAs. The complete schedule of assessments to be obtained during the baseline visit is outlined in **Appendix A**.

Participants who fulfill all the inclusion criteria and none of the exclusion criteria will be randomly assigned on a 1:1:1:1 ratio to one of four treatment groups:

- 5% lidocaine/0.5mg/ml 0.07% estradiol compound vaginal cream + placebo pill
- placebo vaginal cream + nortriptyline pill
- 5% lidocaine/0.5mg/ml 0.07% estradiol compound vaginal cream + nortriptyline pill
- placebo vaginal cream + placebo pill

Medication assignments will be determined by the Duke Clinical Research Institute (DCRI) using randomized blocks, and then stratified by enrollment site. The DCRI will create a SAS program to generate the random sequence that will be loaded in RedCap. Participants and research personnel will be blinded to medication assignment.

[figure not shown]
During the baseline visit, participants will be counseled on optimal study medication administration. Participants will receive a written description of the study with contact numbers of study staff to present to their usual care provider(s).

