15.6 Sample Size and Power

We are planning to enroll 400 women with VBD, with an estimated attrition rate of 20%. Of note, Reed et al. found that vulvar pain measured on a 0-10 numeric scale has standard deviation 2.0.¹⁰⁴ Salaffi et al¹⁰⁵ noted that 2 points on a 0-10 NRS correspond to a clinically meaningful difference in pain severity. Using these results and assuming the within-subject correlation of 0.5, at a significance level of 0.05, the proposed sample size will provide sufficient power of at least 0.80 to detect differences as small as 0.82 on a 0-10 scale for the overall treatment main effects (3 arms) vs. placebo. To test each individual treatment effect vs. placebo, at a significance level of 0.0167 (Bonferroni-corrected for 3 arms), the proposed sample size can detect differences as small as 0.98 on a 0-10 scale. At a significance level of 0.05, the proposed sample size can detect differences as small as 1.35 and 1.20 on a 0-10 scale for the interaction effect of treatment and each VBD-subtype, given possible splits of 40/60, 50/50, or 60/40 (of note, VBD-p vs VBD-c frequencies were 40/60 at UNC and 50/50 at UCLA clinics in previous studies).

To calculate power for research question IIIa, we used data from our previous study of biomarkers in VBD patients.⁷ Conservatively assuming that VBD-c patients represent 60% (192/320) of the sample and VBD-p patients represent 40% (128/320) of the sample, and adjusting the significance threshold for 4 tier 1 cytokine tests, we will be able to detect mean differences of at least 0.4 SD with the power of 0.84 or greater using a t-test. For IL-8, 0.4 SD translates to approximately 2 pg/mL, and for IL-1ra 0.4 SD translates to 240 pg/mL of the minimal detectable difference. Of note, the mean differences between controls and VBD patients for IL-8 and IL-1ra in our previous study were 4 pg/mL and 300 pg/mL, respectively. Thus, we have sufficient power to detect plausible differences in cytokine levels between the VBD subgroups.

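### Section 15.2 runs the active-versus-placebo comparisons only after a significant overall F-test, but the 0.98-point detectable difference in Section 15.6 ignores that step; under the two-step rule, power for combination versus placebo is about 0.70 to 0.79, depending on the effect pattern and the effective sample size

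*Combined protocol and SAP*

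**What the plan says.** Section 15.2 answers question 1a in two steps. One F-test first covers nortriptyline, the cream and their interaction. Then: "If significant ($p < 0.05$), treatment differences (each of 3 treatment groups minus placebo) in the Least-Squares means (LS means), their 2-sided 95% CIs". The sentence goes on to the p-values and the second threshold: "values will be estimated from the MMRM model. P-values will be compared with the significance threshold Bonferroni-corrected for 3 tests (i.e. alpha 0.0166". A comparison with placebo therefore succeeds only if the F-test has p below 0.05 and its own p-value is below 0.0166. As written, the estimates and confidence intervals also exist only if the F-test is significant.

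Section 15.6 gives one figure for each step and none for passing both. For the overall test it claims "sufficient power of at least 0.80 to detect differences as small as 0.82 on a 0-10 scale". For the individual arms it says that "at a significance level of 0.0167 (Bonferroni-corrected for 3 arms), the proposed sample size can detect differences as small as 0.98 on a 0-10 scale". The 0.80 is attached in words to 0.82 and only implied for 0.98.

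**The concern.** Two protections are applied in series. Three tests at 0.0166 already hold the family-wise error at or below 3 × 0.0166 = 0.0498 whatever the F-test does, so for these comparisons the gate can only cancel results that have passed. The probability of passing both steps cannot exceed the probability of passing the second alone, which is what 0.98 describes.

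Two things are at stake. Combination versus placebo may have less power than Section 15.6 implies. And if the F-test misses, the plan specifies no treatment difference or interval for question 1a on the tampon test, a primary endpoint.

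**Working it through.** **Inputs from the documents.** Size and loss: "We are planning to enroll 400 women with VBD, with an estimated attrition rate of 20" per cent (Section 15.6). Allocation: "randomly assigned on a 1:1:1:1 ratio to one of four treatment groups" (Section 5.3), hence 100 randomized and 80 completers per arm. Spread: "vulvar pain measured on a 0-10 numeric scale has standard deviation 2.0". Correlation: "assuming the within-subject correlation of 0.5, at a significance level of 0.05".

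**Assumptions not in the documents.** The F-test has 3 df (three treatment terms at one visit), tests are two-sided, correlation is equal between all visits, and dropout timing and effect patterns are as given below.

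**Step 1: reproduce 0.98 as a stand-alone test.** In large samples the detectable difference is (2.394 + 0.842) × √(2 × 4 / n).
- n = 80 completers: 3.236 × 0.3162 = 1.02. Power at 0.98 is 0.755, so the figure does not reproduce.
- A mixed model that uses partial data from 100 per arm inflates the variance by 1 + 0.25 × (1 − R²), where 0.25 = 0.20/0.80. With three earlier visits R² = 0.375, the factor is 1.156 and the effective n is 86.5. With two earlier visits, as at week 16, R² = 0.333, the factor is 1.167 and the effective n is 85.7.
- Across plausible dropout timings the effective n is 84 to 90, the detectable difference 0.96 to 1.00, and power at 0.98 about 0.78 to 0.82.
- n = 87: 3.236 × 0.3032 = 0.98. The same n gives 0.82 for a 3-df F-test when all three active arms differ equally from placebo. In the additive pattern, the F-test's power at 0.82 is only about 0.61.

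So 0.98 is an ungated pairwise figure at roughly 87 effective participants per arm.

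**Step 2: where the gate can bind.** Any pairwise t satisfies t² ≤ 3F. In large samples F is therefore always significant once |t| exceeds √7.815 = 2.80. Only results with |t| between about 2.39 and 2.80 can be lost, so the loss is bounded.

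**Step 3: size of the loss.** Noncentrality at n = 87:
- Pairwise: 0.98² × 87/8 = 10.44.
- F-test, additive pattern (0, 0.49, 0.49, 0.98): 87 × (2 × 0.49²)/4 = 10.44. The same signal is spread over 3 df.
- F-test, all arms equal: 87 × 0.75 × 0.98²/4 = 15.67.

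Simulated power at a combination effect of 0.98 (the two single-drug effects are in brackets):

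| Pattern | F-test, n = 87 | Pairwise alone, n = 87 | Both steps, n = 87 | Both steps, n = 80 |
|---|---|---|---|---|
| Additive (0.49, 0.49) | 0.776 | 0.795 | 0.745 | 0.701 |
| Subtype-matched, 40/60 (0.39, 0.59) | 0.79 | 0.795 | 0.752 | 0.708 |
| Unequal (0.29, 0.69) | 0.840 | 0.795 | 0.767 | 0.724 |
| Combination only (0, 0) | 0.926 | 0.795 | 0.787 | 0.745 |
| All arms equal (0.98, 0.98) | 0.926 | 0.795 | 0.787 | 0.745 |
| One drug does everything (0.98, 0) | 0.979 | 0.795 | 0.794 | 0.754 |

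At n = 80, pairwise power alone is 0.755 in every row. The subtype-matched row supposes that each drug works only in its own subtype and the combination in both. A 40/60 split then gives 0.4 × 0.98 = 0.39 and 0.6 × 0.98 = 0.59; a 50/50 split gives the additive row.

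**Step 4: error control.** Under the global null, the chance of any false claim is 0.044 with Bonferroni alone and about 0.030 with the gate. If the combination works and both single drugs are null, it is 0.031 either way.

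**Step 5: trials without estimates.** In the additive pattern the gate fails in 1 − 0.776 = 22% of trials (1 − 0.736 = 26% with 80 per arm).

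**Step 6: detectable difference for the two-step rule.** In the additive pattern, power of 0.80 needs about 1.04 points at n = 87, or 1.08 at n = 80.

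**The case against.** An omnibus F-test before pairwise tests is conventional and valid, and it does lower the actual global-null error. A reader might infer that the gate gains nothing in error control. The figures in Step 4 contradict that; what they support is that the gain is not needed to stay under 0.05.

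A reader might also infer that the gate always pushes power well below 0.80. It does not. The loss is about 1 point or less in three of the patterns, and no section predicts exact additivity in the pooled sample. Section 18.3.4 expects synergy, which moves toward the combination-only pattern; with single-drug effects of 0.25 points the loss is about 3 points. Against that, Section 4 expects the subtypes to respond to different drugs, question 1a pools them, and Section 15.6 expects splits near 40/60 or 50/50. Intermediate average effects are therefore a plausible consequence of the trial's own hypotheses.

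The loss also shrinks as effects grow. In the additive pattern power falls from 0.938 to 0.913 at 1.2 points and from 0.994 to 0.990 at 1.5, and not at all at 2 points, which Section 15.6 cites as clinically meaningful. This stands: the cost falls near the printed detectable difference.

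Finally, Section 15.2 states neither the df nor the visit of the F-test, and the model contains treatment-by-visit terms. A different test would change the gated figures.

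**Conclusion.** The point holds in a limited form. Section 15.6 gives no power for the rule that decides question 1a. At 0.98, the gate lowers power for combination versus placebo from about 0.795 to about 0.745 when the two single drugs each give half the effect, with smaller losses as the pattern moves away from that, down to almost none. With 80 completers per arm it falls from 0.755 to between 0.70 and 0.75. The missing estimates and intervals after a failed F-test are a gap whatever the power.

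One tempting conclusion is not supported: that removing the gate makes 0.98 at 0.80 power correct as printed. That rests on an unstated dropout assumption. With a plain 80 completers per arm, the ungated shortfall from 0.80 (about 4.5 points) is nearly as large as the most that the gate takes in these patterns (about 5 points).

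All gated figures rest on a 3-df F-test, SD 2.0, and an effective n of about 87 or 80 per arm.

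**What to change.** In Section 15.2, always estimate the three active-minus-placebo differences with 95% confidence intervals, and test them at the stated Bonferroni threshold (or with Holm's procedure) without requiring a significant F-test. Keep the F-test as supportive, and state its df and visit.

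Leave unchanged whatever role the F-test has in opening the percent-decrease analyses of the tampon test and SF-MPQ later in Section 15.2. Defining a significant 1a as at least one significant pairwise result could narrow that route: when only the combination works at 0.98, the F-test is significant with probability 0.926, against about 0.80 for any pairwise result.

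In Section 15.6, state that 0.82 assumes the same effect in all three active arms, and give the effective sample size or dropout timing behind 0.98. If the gate is kept, give the detectable difference for the two-step rule: about 1.04 in the additive case, or about 1.08 with 80 per arm.

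The cost is wording, with no added participants or data. Pairwise power is never lowered. The actual global-null error rises from about 0.03 to 0.044, still under 0.05.
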